### 6.6.3 Emergency breaking of assigned treatment code

Emergency code breaks must only be undertaken when it is required to do so in order to treat the participant safely. Blinding codes may also be broken after a participant discontinues treatment due to disease progression if deemed essential to allow the investigator to select the participant's next treatment regimen, and after discussion and agreement with the sponsor. Most often, study treatment discontinuation and knowledge of the possible treatment assignments are sufficient to treat a study participant who presents with an emergency condition. Emergency treatment code breaks are performed using the NIRT. When the investigator contacts the system to break a treatment code for a participant, he/she must provide the requested participant identifying information and confirm the necessity to break the treatment code for the participant. The investigator will then receive details of the investigational drug treatment for the specified participant and a fax or email confirming this information. The system will automatically inform the Novartis monitor for the site and the study team that the code has been broken.

It is the investigator's responsibility to ensure that there is a dependable procedure in place to allow access to the NIRT at any time in case of emergency. The investigator will provide:

- protocol number
- study drug name (if available)
- participant number

In addition, oral and written information to the participant must be provided on how to contact his/her backup in cases of emergency, or when he/she is unavailable, to ensure that un-blinding can be performed at any time.

An assessment will be done by the appropriate site personnel and sponsor after an emergency unblinding to assess whether or not study treatment should be discontinued for a given participant and, if applicable, whether the participant can continue with follow up assessments.

## **6.7 Preparation and dispensation**

Each study site will be supplied with study drug in packaging as described under [Section 6.1.1](#) (Investigational and control drugs). Please refer to Pharmacy manual for detailed instructions about study medication preparation and administration.

As per the treatment assigned to the participant, investigator staff will select the study treatment to dispense to the participant. The study medication has a label. A unique medication number is printed on the study medication label.

### **6.7.1 Handling of study treatment and additional treatment**

Study treatment must be received and acknowledged by a designated staff at the study site, handled and stored safely and properly and kept in a secured location to which only the investigator and designated site staff have access. Upon receipt, all study treatment must be stored according to the instructions specified on the labels and in the Pharmacy Manual.

Clinical supplies are to be dispensed only in accordance with the protocol. Technical complaints are to be reported to the respective Novartis Country Organization (CO) Quality Assurance.

An unblinded pharmacist or other qualified and trained site staff are required to prepare the study drug and placebo for administration. Please refer to the pharmacy manual for details.

Medication labels will be in the local language and comply with the legal requirements of each country. They will include storage conditions for the study treatment but no information about the participant except for the medication number.

The investigator must maintain an accurate record of the shipment and dispensing of study treatment in a drug accountability log. Monitoring of drug accountability will be performed by monitors during site visits or remotely and at the completion of the trial.

At the conclusion of the study, and as appropriate during the course of the study, the investigator will return all unused study treatment, packaging, drug labels, and a copy of the completed drug accountability log to the Novartis monitor or to the Novartis address provided in the investigator folder at each site.

In this study there is no additional treatment apart from study treatment.

## 7 Informed consent procedures

Eligible participants may only be included in the study after providing (witnessed, where required by law or regulation), Institutional Review Board (IRB)/Independent Ethics Committee (IEC)-approved informed consent.

Informed consent must be obtained before conducting any study-specific procedures (e.g. all of the procedures described in the protocol). The process of obtaining informed consent must be documented in the participant source documents.

Novartis will provide to investigators in a separate document a proposed ICF that complies with the ICH GCP guidelines and regulatory requirements and is considered appropriate for this study. Any changes to the proposed consent form suggested by the investigator must be agreed by Novartis before submission to the IRB/IEC.

Information about common side effects already known about the investigational drug can be found in the IB. This information will be included in the participant informed consent and should be discussed with the participant during the study as needed. Any new information regarding the safety profile of the investigational drug that is identified between IB updates will be communicated as appropriate, for example, via an Investigator Notification (IN) or an aggregate safety finding. New information might require an update to the informed consent and then must be discussed with the participant.

The following informed consents are included in this study:

- Main study consent, which also include:

Commercially Confidential Information

- As applicable, Pregnancy Outcomes Reporting Consent for female participants  
Commercially Confidential Information

WoCBP must be informed that taking the study treatment may involve unknown risks to the fetus if pregnancy were to occur during the study and agree that in order to participate in the study they must adhere to the contraception requirements.

Commercially Confidential Information

A copy of the approved version of all consent forms must be provided to Novartis after IRB/IEC approval.

Participants might be asked to complete an optional questionnaire to provide feedback on their clinical trial experience.

## 8 Visit schedule and assessments

The Assessment Schedule lists all of the assessments and when they are performed. All data obtained from these assessments must be supported in the participant's source documentation.

Participants should be seen for all visits/assessments as outlined in the assessment schedule or as close to the designated day/time as possible. Missed or rescheduled visits should not lead to automatic discontinuation. Participants who prematurely discontinue the study for any reason should be scheduled for a visit as soon as possible, at which time all of the assessments listed for the final visit will be performed (EoS/Early discontinuation visit). At this final visit, all dispensed investigational product should be reconciled, and the adverse event and concomitant medications should be recorded on the eCRF.

If the COVID-19 pandemic limits or prevents on-site study visits, alternative methods of providing continuing care may be implemented. Phone calls, virtual contacts (e.g. teleconsultation) or visits by site staff/home nursing service to the participant's home depending on local regulations and capabilities, can replace on-site study visits, for the duration of the pandemic until it is safe for the participant to visit the site again.

Commercially Confidential Information

## 8.1 Screening

If participant failed initial screening, re-screening of the participant is allowed after consultation with Sponsor.

In the case where a safety laboratory assessment at screening and/or baseline is outside of the range specified in the exclusion criteria, the assessment may be repeated once prior to randomization. If the repeat value remains outside of the specified ranges, the participant must be excluded from the study.

Local guidelines and regulations need to be strictly followed regarding the screening and monitoring of the SARS-CoV-2 (COVID-19).

### 8.1.1 Eligibility screening

#### 8.1.1.1 Hepatitis screen, HIV screen

All participants will be screened for Hepatitis B surface antigen (HBsAg) and hepatitis B core antibody (anti-HBc).

Screening for Hepatitis C will be based in HCV antibodies and if positive, HCV RNA levels should be determined.

Evaluation for HIV seropositivity will be performed, and, if positive, confirmation by a second technique available at the laboratory site e.g. Polymerase Chain Reaction.

Appropriate counseling will be made available by the Investigator in the event of a positive confirmatory test. Notification of state and federal authorities, as required by law, will be the responsibility of the Investigator. Results will be available as source data and will not be recorded within the eCRF. All samples will be shipped to the central laboratory.

#### 8.1.1.2 Quantiferon Test

Blood tuberculosis testing with the Quantiferon assay (QuantiFERON®-TB Gold In-Tube) will be performed as specified in the Assessment schedule in [Section 8](#). For the details regarding sample preparation and shipment please refer to the laboratory manual.

Note: if Quantiferon test is indeterminate, it may be repeated once. Two indeterminate Quantiferon tests will be considered as evidence of TB infection. Furthermore, after anti-TB treatment, participants with history of or latent TB may become eligible according to national guidelines.

Any significant findings will be recorded in the "Relevant medical history/Current medical conditions" section of the eCRF.

#### 8.1.2 Information to be collected on screening failures

Participants who sign an ICF and are subsequently found to be ineligible prior to randomization will be considered a screen failure. The visit date, demographic information, informed consent (and withdrawal of informed consent, if applicable), SAE, Death (if applicable) pages must also be completed for screen failure participants who experience SAE. No other data will be entered into the clinical database for participants who are screen failures and experience no SAE. (see

[Section 10.1.3](#). SAE reporting for details). If the participant fails to be randomized, the NIRT must be notified within 2 days of the screen failure that the participant was not randomized.

Participants who are randomized and fail to start treatment, e.g. participants randomized in error, will be considered early terminators. The reason for early termination should be recorded on the appropriate eCRF.

## 8.2 Participant demographics/other baseline characteristics

Participant demographics: age, sex, race, predominant ethnicity (if permitted) and relevant medical history/current medical conditions (until date of signature of informed consent) will be recorded in the eCRF. Where possible, the diagnosis and not symptoms should be recorded.

All prescription medications, over-the-counter drugs and significant non-drug therapies prior to the start of the study must be documented. See the protocol [Section 6.2.1](#) for further details on what information must be recorded on the appropriate page of the eCRF.

## 8.3 Efficacy

Severity of AD will be measured by Clinical Outcomes Assessments (COAs) such as IGA (Investigator Global Assessment); Commercially Confidential Information

The primary endpoint is IGA response at week 16.

Commercially Confidential Information

### 8.3.1 IGA

The IGA scale used in the study is vIGA-AD™ (Validated Investigator Global Assessment scale for Atopic Dermatitis). The IGA rating scale is used to determine the severity of AD symptoms and clinical response to treatment. It reflects a participant's overall disease severity for the whole body based on a 5-point scale. The 5-point scale includes: clear, almost clear, mild, moderate, and severe disease.

IGA response is defined as clear or almost clear after week 16 with at least a 2 point-reduction from baseline.

The scale is a static scale and does not refer to previous status of the participant. The Investigator or trained qualified designee will complete the IGA assessment on each of the visits as outlined in the Assessment Schedule. Whenever possible, the IGA assessments should be performed by the same evaluator throughout the study.

The IGA should always be conducted as the first clinical assessment, CCI  
. It must be based on a whole body skin inspection.

**Table 8-4** Investigator Global Assessment (IGA)

| Score                   | Morphological Description  |
|-------------------------|--|
| 0 - Clear        | No inflammatory signs of atopic dermatitis (no erythema, no lichenification, no oozing/crusting). Postinflammatory hyperpigmentation and/or hypopigmentation may be present. |
| 1 - Almost Clear | Barely perceptible erythema, barely perceptible induration/papulation, and/or minimal lichenification. No oozing or crusting.  |
| 2- Mild          | Slight but definite erythema (pink), slight but definite induration/papulation, and/or slight but definite lichenification. No oozing or crusting.                           |
| 3 - Moderate     | Clearly perceptible erythema (dull red), clearly perceptible induration/papulation, and/or clearly perceptible lichenification. Oozing and crusting may be present.          |
| 4 - Severe       | Marked erythema (deep and bright red), marked induration/papulation, and/or marked lichenification. Disease is widespread in extent. Oozing or crusting may be present.      |

Commercially Confidential Information

### 8.3.4 Appropriateness of efficacy assessments

The efficacy measurements included in this study have been and are used in clinical trials evaluating efficacy in AD and are standard for this indication ([Eichenfield et al 2014](#), [Simpson et al 2016](#), [Beck et al 2014](#), [Chopra and Silverberg 2018](#)).

## 8.4 Safety

Safety assessments are specified below with the assessment schedule detailing when each assessment is to be performed.

During the COVID-19 pandemic that limits or prevents on-site study visits regular phone or virtual calls may occur (every 4 weeks or more frequently if needed) for safety monitoring and discussion of the participant's health status until the participant can again visit the site.

For details on AE collection and reporting, refer to [Section 10.1.1](#) Adverse Events.

| Assessment                  | Specification   |
|-----------------------------|---|
| Physical examination | 
A complete physical examination will include the examination of general appearance, skin, neck (including thyroid), eyes, ears, nose, throat, lungs, heart, abdomen, back, lymph nodes, extremities, vascular, and neurological. If indicated based on medical history and/or symptoms, rectal, external genitalia, breast, and pelvic exams will be performed.
 
A short physical exam will include the examination of general appearance and vital signs (Systolic and Diastolic Blood pressure [SBP and DBP] and pulse). A short physical exam will be done at Day 29 visit except at visit at Baseline/Day 1 and at Day 113 when complete physical examination will be completed.
 
Information for all physical examinations must be included in the source documentation at the study site. Clinically relevant findings that are present prior to signing informed consent must be recorded on the appropriate eCRF that captures medical history. Significant findings made after signing informed consent which meet the definition of an Adverse Event must be recorded as an adverse event.
 |

| Assessment               | Specification  |
|--------------------------|--|
| Vital signs       | 
Vital signs will include the collection of tympanic body temperature (recorded in °C), blood pressure (BP) and pulse measurements.
 
After the participant has been sitting for 3 minutes, with back supported and both feet placed on the floor, systolic and diastolic BP will be measured using an automated validated device, with an appropriately sized cuff. In case the cuff sizes available are not large enough for the participant's arm circumference, a sphygmomanometer with an appropriately sized cuff may be used.
 
If vital signs are out-of-range at screening and/or baseline two additional readings can be obtained, so that up to three consecutive assessments are made, with the participant seated quietly for approximately five minutes preceding each repeat assessment.
 
In case of repeated vital assessments, the eCRF should contain all repeat measurements.
 |
| Height and weight | 
Height is obtained in centimeters (cm) and body weight is obtained in kilograms (kg) and rounded to the nearest 0.1 kg. Weight is obtained in indoor clothing, without shoes.
 
Body mass index (BMI) will be calculated using the following formula:
 

• <math>BMI = \text{Body weight (kg)} / [\text{Height (m)}]^2</math>

 
Screening visit weight will be used for dose calculations by the pharmacist.
   |

#### 8.4.1 Laboratory evaluations

In the case where a laboratory range is not specified by the protocol, but a value is outside the reference range for the laboratory at screening and/or initial baseline, a decision regarding whether the result is of clinical significance or not shall be made by the Investigator (in consultation with the sponsor, if considered relevant by PI) and shall be based, in part, upon the nature and degree of the observed abnormality. The assessment may be repeated once prior to randomization.

In all cases, the Investigator must document in the source documents the clinical considerations (i.e., result was/was not clinically significant and/or medically relevant) in allowing or disallowing the participant to continue in the study.

A central laboratory will be used for analysis of all safety specimens collected. In case of need for clarification or follow-up on adverse event or liver/renal event, local laboratory might be used in addition to central laboratory assessment. Results from all local laboratory re-testing should be entered in appropriate eCRF pages. Details on the collection, shipment of samples and reporting of results by the central laboratory are provided to investigators in the central laboratory manual.

Participants should be reminded to fast (having had their last meal the evening, approx. 6-12 hours before visit) at all visits before coming to the site for clinical chemistry blood sample.

## Clinical Chemistry

A midstream urine sample (approx. 30 mL) will be obtained, in order to avoid contamination with epithelial cells and sediments, and allow proper assessments.

| Test Category                    | Test Name   |
|----------------------------------|---|
| Hematology                | Hemoglobin, hematocrit, red blood cell (RBC) count, white blood cell (WBC) count with differentials (neutrophils, basophils, eosinophils, monocytes, lymphocytes) and platelet count  |
| Chemistry                 | 
The chemistry panel (fasting at all visits) will include: albumin, alkaline phosphatase, total and differentiated bilirubin, calcium, chloride, serum bicarbonate, creatinine, creatine kinase (CK), aspartate aminotransferase (AST), alanine aminotransferase (ALT), <math>\alpha</math>-amylase, <math>\gamma</math>- glutamyltransferase (GGT), glucose, sodium, potassium, inorganic phosphorus, total protein, lactate dehydrogenase (LDH), magnesium, blood urea nitrogen (BUN), uric acid, lipase, triglycerides, cholesterol (direct LDL, HDL cholesterol and LDL cholesterol) and serum ketones.
 
The chemistry panel will also include total immunoglobulin E (IgE) and high sensitivity C-reactive Protein (CRP) as specific markers for AD.
 |
| Urinalysis                | Semi-quantitative 'dipstick' evaluation of the urine for the following parameters will be performed centrally: specific gravity, pH, glucose, protein, bilirubin, ketones, nitrite, leukocytes and blood. If the dipstick result is positive for nitrite, leucocytes and/or blood, microscopic analysis will be done (including white blood cells, red blood cells and casts). Urine culture and sensitivity test may be performed locally as per investigator's discretion.  |
| Hepatitis and HIV markers | anti-HIV antibody, HBsAg, anti-HBc, anti-HCV, HCV RNA(if applicable)  |
| Pregnancy test            | Serum / Urine pregnancy test (refer to Section 8.4.3 Pregnancy and assessments of fertility)  |

#### **8.4.2      Electrocardiogram (ECG)**

ECGs will be analyzed locally and performed with ECG machines at the investigator sites. Investigator sites will follow their own procedures relating to the ECG collection and reporting.

The Fridericia QT correction formula (QTcF) must be used for clinical decisions.

$$QTcF = \frac{QT}{\sqrt[3]{RR}}$$

Single 12-lead ECGs are collected and results are entered into the appropriate eCRF page. The original ECGs appropriately signed, must be collected and archived at the study site.

Each ECG tracing must be labeled with study number, participant initials, participant number, date and time, and filed in the study site source documents. Investigator should document clinical evaluation in source. For any ECGs with participant safety concerns, two additional ECGs must be performed to confirm the safety finding. Clinically significant ECG findings at baseline must be discussed with the sponsor before administration of study treatment.

Clinically significant abnormalities must be recorded on the relevant section of the medical history/Current medical conditions/AE eCRF as appropriate.

#### **8.4.3      Pregnancy and assessments of fertility**

All WoCBP will have pregnancy testing during the study until EoS at the defined assessment visits. As additional follow up period is required for screening of pregnancy, a monthly urinary pregnancy test must be conducted for 6 months after the last dose of study drug. More urinary tests can be done at the discretion of the investigator. A home urine pregnancy test kit will be provided to participants by the site.

WoCBP should be instructed to use highly effective contraception during the study and after EoS (for 6 months after the last dose of study drug).

At EoS, the site will ask the participant to conduct the pregnancy test(s) as defined in assessment schedule [Table 8-3](#) and will call the patient to remind her. The participant should communicate the results of the pregnancy test(s) to the site. A positive pregnancy test must trigger a pregnancy report to the sponsor (see [Section 10.1.4](#)). If pregnancy is discovered after EoS, the participant should be asked to come for a visit to the site and to read and sign the pregnancy consent form to allow the Study Doctor to ask about her pregnancy.

### **Assessments of fertility:**

Medical documentation of oophorectomy, hysterectomy, or tubal ligation must be retained as source documents. Subsequent hormone level assessment to confirm the woman is not of child-bearing potential must also be available as source documentation in the following cases:

1. Surgical bilateral oophorectomy without a hysterectomy.
2. Reported 12 months of natural (spontaneous) amenorrhea with an appropriate clinical profile.

In the absence of the above medical documentation, Follicle Stimulating Hormone (FSH) testing is required of any female participant regardless of reported reproductive/menopausal status at screening.

#### **8.4.4 Appropriateness of safety measurements**

The safety assessments selected are standard for this indication/participant population.

#### **8.5 Additional assessments**

Commercially Confidential Information

## 9 Study discontinuation and completion

### 9.1 Discontinuation and completion

#### 9.1.1 Study treatment discontinuation and study discontinuation

Discontinuation of study treatment for a participant occurs when study treatment is stopped earlier than the protocol planned duration and can be initiated by either the participant or the investigator.

The investigator must discontinue study treatment for a given participant if, he/she believes that continuation would negatively impact the participant's well-being.

Study treatment must be discontinued under the following circumstances:

- Participant/guardian decision
- Pregnancy
- Use of prohibited treatment as per recommendations in the prohibited medication [Section 6.2.2](#) and rescue medication [Section 6.2.3](#)
- Any situation in which study participation might result in a safety risk to the participant
- Following emergency unblinding
- Severe hypersensitivity reaction occurs, including any of the following: anaphylaxis, fever, chills, urticaria, dyspnea, headache, myalgia, hypotension. Immediate interruption of the infusion or injection to administer study treatment is required in such cases.
- For liver events, please see [Section 10.2.1](#). For renal events, please see [Section 10.2.2](#)
- If a liver or renal event occurs, follow guidelines outlined in [Section 16.2](#) and [Section 16.3](#) regarding discontinuation of study treatment.

The reasons for treatment discontinuation must be collected in line with the intercurrent events introduced in [Section 2.1](#) and the "treatment" attribute described in [Section 2](#) and [Section 6](#).

If discontinuation of study treatment occurs, the investigator should make a reasonable effort to understand the primary reason for the participant's premature discontinuation of study treatment and record this information.

Participants who discontinue study treatment or who decide they do not wish to participate in the study further should NOT be considered withdrawn from the study UNLESS they withdraw their consent (see [Section 9.1.2](#) 'Withdrawal of Informed Consent' section). Where possible, they should return for the assessments indicated in the Assessment Schedule in [Section 8](#). If they fail to return for these assessments for unknown reasons, every effort (e.g. telephone, e-mail, letter) should be made to contact the participant/pre-designated contact as specified in the lost to follow-up section ([Section 9.1.3](#)). This contact should preferably be done according to the study visit schedule.

If the participant cannot or is unwilling to attend any visit(s), the site staff should maintain regular telephone contact with the participant, or with a person pre-designated by the participant. This telephone contact should preferably be done according to the study visit schedule.

After study treatment discontinuation, at a minimum, in abbreviated visits, the following data should be collected at clinic visits or via telephone/email contact:

- New / concomitant treatments
- Adverse Events / Serious Adverse Events

The investigator must also contact the NIRT to register the participant's discontinuation from study treatment.

If discontinuation occurs because treatment code has been broken, please refer to Emergency breaking of treatment code [Section 6.6.3](#).

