For the intercurrent events 1 to 4, a composite strategy will be used: use of any therapy (prohibited or rescue medication taken after the first 6 weeks) as well as any study treatment discontinuation due to lack of efficacy or due to AE related to AD are considered as unfavorable outcome, i.e. the participant will be treated as a non-responder.

For the intercurrent events 5 to 6, a treatment policy strategy will be used and the intercurrent event will be ignored.

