**Handling of remaining intercurrent events:**

1. Relevant use of rescue therapy (after first 6 weeks of treatment)
2. Relevant use of prohibited medication to treat AD symptoms or with impact on efficacy
3. Study treatment discontinuation due to lack of efficacy
4. Study treatment discontinuation due to AE related to AD, e.g. worsening of AD
5. Study treatment discontinuation due to AE not related to AD or due to lack of tolerability
6. Study treatment discontinuation due to other reasons (e.g. administrative if participant relocates to a region where the trial is not offered, or withdrawal of informed consent)

For the intercurrent events 1 to 4, a composite strategy will be used: use of any therapy (prohibited or rescue medication taken after the first 6 weeks) as well as any study treatment discontinuation due to lack of efficacy or due to AE related to AD are considered as unfavorable outcome, i.e. the participant will be treated as a non-responder.

For the intercurrent events 5 to 6, a treatment policy strategy will be used and the intercurrent event will be ignored (set data after discontinuation to be missing)

**The summary measure:** treatment difference of the CMK389 and placebo in absolute responder rates.

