#### **6.1.3.2 Handling of missing values not related to intercurrent event**

For the primary endpoint analysis, there will be no planned imputation of missing data.

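### The SAP names a treatment-policy strategy for intercurrent events 5 and 6 but sets data after discontinuation to missing, so the primary analysis becomes a complete-case estimate

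*Protocol*

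**What the plan says.** **Estimand.** Protocol 2.1 states: "For the intercurrent events 5 to 6, a treatment policy strategy will be used and the intercurrent event will be ignored". Protocol 12.4.3 repeats this. Event 5 is stopping for an adverse event unrelated to atopic dermatitis or for poor tolerability. Event 6 is stopping for other reasons, with withdrawal of consent among the examples. Events 1 to 4 are composite: those participants count as non-responders.

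**Analysis.** SAP 6.1.1, under the handling of intercurrent events, names the same strategy for events 5 and 6 but continues: "the intercurrent event will be ignored (set data after discontinuation to be missing". SAP 6.1.3.1 says that these events are ignored and that nothing needs to be carried forward. For the primary endpoint, SAP 6.1.3.2 says "there will be no planned imputation of missing data".

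**Collection.** For participants who stop treatment, protocol 9.1.1 first says: "Where possible, they should return for the assessments indicated in the Assessment Schedule". It then sets a floor: "After study treatment discontinuation, at a minimum, in abbreviated visits, the following data should be collected at clinic visits or via telephone/email contact". The floor has two items, "New / concomitant treatments" and "Adverse Events / Serious Adverse Events". On the IGA, protocol 8.3.1 says: "It must be based on a whole body skin inspection".

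**The concern.** Under a treatment-policy strategy the outcome at the planned time point is used even though treatment stopped. Setting that outcome to missing is the opposite instruction. With no imputation, a participant who stops before Week 16 for event 5 or 6 contributes no response, and the comparison rests on those who stayed on treatment plus those set to non-response under events 1 to 4. That is a different quantity from the estimand in protocol 2.1. It is biased if stopping is related both to arm and to how the participant would have responded. Stopping for tolerability could well be so related.

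The powered comparison has 32 participants against 16, so a handful of lost outcomes can move the estimate visibly.

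**Working it through.** **Step 1: set the rules side by side.** Take a participant who stops before Week 16 for event 5 or 6 and has no event of type 1 to 4.

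| Situation at Week 16 | Protocol 2.1 and 12.4.3 | SAP 6.1.1 with 6.1.3.2 |
|---|---|---|
| Attends, IGA rated | Rating is used | Set to missing, not imputed |
| Minimum contact only, no IGA | No rating to use | Missing, not imputed |
| Consent withdrawn (protocol 9.1.2) | No rating to use | Missing, not imputed |

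The first row is a direct contradiction. In the second row the outcome is lost at collection: the floor in 9.1.1 does not list the IGA, and a telephone or email contact cannot replace a whole-body inspection. In the third row no collection rule can help, so a stated analysis method is needed.

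**Step 2: illustrate the size.** The documents give no figure for events 5 and 6, so there is no plan figure to reproduce.
- From protocol 12.8.1: 32 on CMK389 i.v., 16 on pooled placebo, placebo rate 7%, difference 36 points, so an active rate of 7 + 36 = 43%.
- Assumed: 3 of 32 and 2 of 16 have no usable Week 16 IGA, leaving 29 and 14. Observed responders are 12 and 1, close to the planning rates.

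Results:
- Complete case: 12/29 − 1/14 = 41.4% − 7.1% = 34.2 points (from unrounded rates).
- Least favourable (missing active fail, missing placebo respond): 12/32 − 3/16 = 37.5% − 18.75% = 18.8 points.
- Most favourable (missing active respond, missing placebo fail): 15/32 − 1/16 = 46.9% − 6.25% = 40.6 points.
- All missing counted as non-responders: 12/32 − 1/16 = 37.5% − 6.25% = 31.25 points.

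Five participants therefore leave a range of 40.6 − 18.8, about 22 points, against a planned effect of 36.

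**Step 3: one direction of bias.** Suppose that the true treatment-policy rate on active is 43%, that a fraction d of the active arm is missing, and that those participants would have responded at the 7% placebo rate. The rate among the observed is (0.43 − 0.07d)/(1 − d).
- d = 5%: 0.4265/0.95 = 44.9%, or 1.9 points too high.
- d = 10%: 0.423/0.90 = 47.0%, or 4.0 points too high.
- d = 20%: 0.416/0.80 = 52.0%, or 9.0 points too high.

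Both d and the 7% response rate among those who stop are assumptions.

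**The case against.** **The protocol already asks for the IGA.** A reader might infer from the two-item list that the protocol never seeks the primary endpoint after discontinuation. The text does not support that. Protocol 9.1.1 first asks for return to the scheduled assessments, and the IGA belongs to that schedule. The list is a floor, placed after the paragraph on participants who cannot or will not attend. What stands is narrower: the floor also covers abbreviated clinic visits and does not name the IGA there. The schedule tables are redacted, so the exact IGA visits cannot be checked.

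**There is an early-discontinuation visit.** Protocol section 8 provides final-visit assessments for those who leave the study early. That visit is held promptly, so it need not fall at Week 16, and the SAP carries nothing forward.

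**The SAP parenthesis may mean only that uncollected data stay missing.** SAP 6.1.3.1, which merely rules out carry-forward, fits that reading. But the words in 6.1.1 instruct that data be set to missing, and a programmer would follow them. If the milder meaning was intended, the sentence still has to change.

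**Replacement.** Protocol 9.1.1.1 allows replacement up to 64 evaluable participants. That restores numbers, not the outcomes of those who stopped. Because evaluability depends on doses received and on end-of-treatment data, it does not remove selection.

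**The numbers.** The missing counts are assumed, and the bounds are extremes, not an expected bias. A reader might also infer that the 80% probability of success in protocol 12.8.1 is undermined. That cannot be shown: the dual-criterion thresholds and the placebo prior are redacted, and replacement would offset some loss of numbers.

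**Conclusion.** SAP 6.1.1 is wrong as written. Its rule for events 5 and 6 contradicts the strategy it names and the estimand in protocol 2.1 and 12.4.3. Together with the absence of imputation, it makes the primary result a complete-case estimate with respect to these events. This follows from unredacted text. It assumes that the redacted model in SAP 6.1.3 does not restore the discarded outcomes in some other way.

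The omission of the IGA from the minimum in protocol 9.1.1 is a supporting weakness, not the main defect. While the SAP rule stands, collecting more IGAs would change nothing.

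The size is unknown. With five assumed missing outcomes, a 34.2-point difference is bounded by 18.8 and 40.6 points; with none missing, the issue has no numerical effect. The trial is a non-confirmatory proof of concept, so this should be corrected but does not invalidate the design.

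**What to change.** 1. **SAP 6.1.1:** delete the parenthesis that sets post-discontinuation data to missing. State that for events 5 and 6 the observed Week 16 IGA is used regardless of discontinuation, and align 6.1.3.1. The composite rule for events 1 to 4 is unchanged.
2. **SAP 6.1.3.2:** for participants with no obtainable Week 16 IGA, such as those who withdrew consent, add a simple sensitivity analysis: non-responder imputation, with best-case and worst-case bounds as in the working above.
3. **Protocol 9.1.1:** state that participants who stop treatment without withdrawing consent should have the IGA at the scheduled Week 16 visit whenever they attend in person. Word it separately from the items that telephone or email can supply. No medication item is needed, because concomitant treatments, which include rescue use, are already in the minimum.

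The first change matters most, because without it collected ratings are still discarded. The cost is a few sentences in two documents, one small extra table, and one already scheduled visit for a few participants. Those who will not attend remain missing, and the second change covers them.
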